8	Send mass mailing to identify interested providers	6-10			X			
9	Enroll/randomize providers (Intervention Time 0 (I0))	6-10			X	X		
10	Collect baseline practice data online	7-23					X	
11	Complete practice run-in phase data (exit cards)	7-23					X	
12	Send repeated emails to dentist/hygienist for retention	7-23			X		X	X
13	Collect usage data from websites	7-23	X		X		X	X
14	Have practice enroll patients through Refer2Quit	7-23			X	X		
15	Send provider reports of patient enrollment	7-23				X	X	
16	Measure Referral Rates at baseline, 6 and 12 months after practice enrollment using patient exit card surveys (first cards collected in run-in phase)	7-12					X	H1
17	Measure number of referrals using Refer2Quit and Information prescriptions	7-23						H1
18	Measure rates of patients who GO to Decide2Quit	7-23					X	H2
19	Measure patient QUIT rates, quit attempts, and readiness to quit at 6 months (telephone follow-up)	10-30						H3
20	Validate 6-month quit with Cotinine*	10-30					X	H3
21	Test Hypotheses, prepare manuscripts	10-36						X

\*Mailed salivary cotinine (Salimetrics); H1 = Hypothesis1; H2 = Hypothesis 2; H3 = Hypothesis 3 (See D5 for details of Measures)

To further clarify the flow of the development, intervention, and evaluation, Figure 3 below summarizes the planned timeline for accomplishing key tasks.

[figure not shown]

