interviews. However, these delayed reports of provider performance may suffer from recall bias due to time elapsed from the patient visit to the time of follow-up assessment. Immediate exit interviews for smoking cessation have been found to correlate with audiotapes.

In DTC.Net, we have developed and evaluated patient-reported provider performance measures that are completed and collected and the time of the visit on “Exit Cards.” These patient Exit Cards – brief surveys completed by patients at the end of their appointment – were developed using principles of ecological momentary assessment (EMA). EMA is a method used in health behavior and more recently in health services research to overcome limitations of traditional self-report assessments.

Practices will be provided a set of 100 patient exit cards at each assessment interval. As a baseline, practices will be provided 50 cards in the run-in phase. At each practice, exit cards will be distributed by office staff to consecutive patients (19 and over). Eligible patients will be adults who have completed their visit. In a pilot study for DTC.Net, patients were asked to record the time required to complete the pilot survey. The average time to complete was two minutes and ranged from one to three. The exit cards are administered while the patient is awaiting follow-up instructions and completing payment. A brief statement is included explaining the study, indicating that participation is voluntary, and that their responses will not influence the care that they receive. Importantly, participation is anonymous and no patient identifiers will be included on the Exit Cards. This recruitment is solely to assess provider performance and no patient follow-up is needed.

Each patient is provided a pen to help complete the survey and as a gift. Patients place completed exit cards in an accompanying envelope and then deposit in a sealed collection box. If a patient is not interested in completing the exit card, they write “declined” and return the card to the box. When all exit cards are distributed, the practice returns the collection box to our coordinating center. For each set of 100 exit cards, we estimate 20 to 25 tobacco users will be identified.

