The exit card will contain brief questions used to assess whether the patient was a tobacco user and whether the provider **Referred** the patient. We will also assess age, gender, other components of the 5A’s, and stage of change: a part of the Transtheoretical Model of behavior change.

We will provide a small reimbursement for data collection (visa debit cards) to the office staff as remuneration for their assistance in distributing exit cards (see budget justification). As discussed in our preliminary data above, from 19,000 exit cards distributed for DTC.Net the response rate has been over 85%.

We had considered collecting exit cards on only smokers, but 1) prior experience with these cards indicates that any instructions other than simply consecutive patients dramatically reduces practices’ ability to complete the data collection and 2) in addition to assessing Refer, we also want to assess rates of Ask (screening for smoking by staff) and Advise (staff advising tobacco users to quit). For the assessment of Ask, we need both smokers and non-smokers.

**Patient Recruitment Part 2: Website** - We will recruit through the website in two layers. First, as they enter the website, patients will be informed that we will monitor use of the website and that reports of total number of uses will be returned to their providers. All patients will be asked to identify their provider (using a unique ID) so that we can provide feedback reports to providers and have data for hypothesis 2. Second, patients will be asked to agree to a six-month follow-up telephone survey similar to the patient exit cards (hypothesis 3). Those who agree will be asked to provide contact information including a phone number and name, again through a SSL online form. Because we want to have as many patients participate in Decide2Quit as possible, we will not require agreement to follow-up as a prerequisite to using the site.

	Intervention			Control		
	Total N	N	%	Total N	n	%
Start with 1,000 patient visits						
Total Smokers	1000	200	20%	1000	200	20%
% of Smokers Referred	200	48	24%	200	24	12%
% of Smokers Referred who GO	48	19	40%	24	4.8	20%
% of Smokers that GO who QUIT	19	3	15%	5	0.5	10%

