Unit of Inference. Our unit of randomization is at the practice level, but, all our outcomes are assessed at the patient level. With data at the patient level, we have the flexibility to set our unit of inference at the practice level, or at the patient level (with the second two using modeling techniques to account for clustering). We have carefully considered the unit of inference for each hypothesis. A recent article by Donner discusses the unit of inference and notes that it is often most appropriately set at the unit where the effect is most important to the investigators. As discussed, the HI-QUIT intervention is designed to target all aspects of the clinical microsystem (patients, providers, and processes within the practice). Both dentists and hygienists will have a role in implementing the system and it is anticipated that the roles of dentists and hygienists in Refer2Quit will vary from microsystem to microsystem – although we anticipate that hygienists will usually be the driving force behind Refer2Quit. Considering the unit of inference is particularly important for Hypothesis 1, assessing rates of referral. There are multiple sources of effects, including the providers and patients. Thus, our analysis should be designed to evaluate these sources. We will use hierarchical modeling to explicitly test the sources of variance in using HI-QUIT.

**Hypothesis 1: The proportion of patients Referred to self-management resource websites will be larger in HI-QUIT practices (24% of smokers) compared to control practices (12% of smokers).**

Data Definitions for Hypothesis 1 (H1): The main dependent variable is the dichotomous outcome of “Refer”, indicating whether a patient is referred, as ascertained by the patient exit cards at discreet intervals (6 and 12 months). As secondary dependent variables, we will also test differences in the other provider performance measures assessed by the exit card (screening for tobacco use, provider advice to quit). The primary independent variable is assignment to intervention or control. Considering the unit of inference is particularly important for Hypothesis 1 (assessing rates of referral). There are multiple sources of effects, including the

Principal Investigator/Program Director (Last, First, Middle): DPBRN c/o [name]

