providers and patients. Thus, our analysis should be designed to evaluate these sources. To this end we will use multilevel modeling to explicitly evaluate the sources of variability in HI-QUIT usage.

Analyses for H1: We will assess differences between intervention and control in three ways.

As our **primary analysis**, we will use patient-level data and multilevel modeling to account for practice-level effects and adjusting for the complex effects of patient and provider variables in multivariable analyses. We have chosen this as the primary analysis for two reasons: 1) because this analysis represents a detailed understanding of the effects of the clinical microsystem intervention, and 2) because we have empirically-driven intraclass correlation coefficients to guide our power calculations.

Thus, to test the overall effect of HI-QUIT, we will use data from all post-intervention evaluation time points together. The hypothesis will be tested by using logistic regression, using patient-level data and incorporating practice-membership as a design factor. An important consideration in handling correlated data resulting from group-randomization is properly accounting for the correlations in the analysis. For example, positive correlations will result in the underestimation of standard errors of the between-practice effects and overestimation of the standard errors of the within-subject effects. Generalized Estimating Equations (GEE), specifically designed for correlated outcomes that can be modeled with a generalized linear model (GLM) including logistic regression, will be used. PROC GENMOD can easily accommodate GEE methods adjusting for clustering. For multivariable analyses logistic regression will be used again, with accounting for clustering. These models will allow adjustment for patient and practice variables described in Section D7. We will also test the hypothesis using data from each individual time point.

**Hypothesis 2: The proportion of patients referred who GO to the patient self-management website will be larger in HI-QUIT practices (40%) compared to control practices (20%).**

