- 2) We assume that only two providers per practice will be actively involved in referring patients. Thus, for some practices more providers may participate and the number of patients referred (say if four hygienists and dental assistants refer) may be considerably greater.

**Hypothesis 1:** This analysis will test whether HI-QUIT practices refer patients at a higher rate than control practices. The literature supports estimating the mean baseline referral rate of 12% for control practices.

Power was estimated using a two-sided chi-square test for a difference in proportions with a Type 1 error rate of 0.05. To take a conservative approach, power was calculated assuming an average of 66 smokers per practice responding to the exit cards. Due to

H1: Number of subjects needed per group for 80% power with a two-sided $\chi^2$ test of equal proportions and $\alpha=0.05$ , adjusting for clustering in practices				
	1	2	3	4
Control proportion, $\pi_1$	0.12	0.12	0.12	0.12
HI-QUIT proportion, $\pi_2$	0.24	0.22	0.20	0.19
Unadjusted n needed per group	176	240	354	447
Adjusted n needed per group*	1,892	2,580	2,805	4805
Number of practices needed per group	29	39	58	73

\* Design factor (  $D = [1 + (m-1) r]$ ) inflates n to account for clustering

clustering within practices and clustering within providers, these will not all be independent observations. The standard practice is to adjust the sample size by an inflation factor  $D = [1 + (m-1) r]$  where r is the intra-class (practice-level) correlation (ICC) and m is the number of subjects per group (practice). Pilot data from DTC.Net revealed a relatively large ICC of 0.15 for rates of advice to quit smoking within dental practices. Assuming equal ICCs of 0.15 for Refer and a cluster size of 66 smokers per practice gives  $D= 10.75$ , or an effective sample size per practice of approximately 6 patients. With these numbers only 29 practices per arm are required to achieve 80% power to detect a significant difference in referral rates of 0.12.

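### H1 is sized on 66 exit-card smokers per practice, presented as conservative, but the planned cards give 40–50; the need rises slightly, from 29 to 30–31 practices per arm, and one table entry and one timeline cell are wrong

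*Protocol*

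**What the plan says.** D10, Hypothesis 1: "Power was estimated using a two-sided chi-square test for a difference in proportions with a Type 1 error rate of 0.05". The same paragraph says that "power was calculated assuming an average of 66 smokers per practice responding to the exit cards", introduces this as a conservative choice, and applies D = 1 + (m − 1)r with r = 0.15, which gives D = 10.75. It concludes that "only 29 practices per arm are required to achieve 80% power" for 24% against 12%. The H1 table gives 29, 39, 58 and 73 practices per group for intervention rates of 24%, 22%, 20% and 19%.

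The number of cards is set under Patient Recruitment Part 1 (Exit Card Surveys): 100 cards per practice at each assessment and 50 in the run-in. On yield it says: "For each set of 100 exit cards, we estimate 20 to 25 tobacco users will be identified".

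D9 takes the H1 outcome from the 6- and 12-month cards and states for the primary analysis that "we will use data from all post-intervention evaluation time points together".

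Table 6, task 16, measures referral "at baseline, 6 and 12 months after practice enrollment using patient exit card surveys (first cards collected in run-in phase" and assigns it to study months 7–12. Task 9 enrols practices in months 6–10.

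**The concern.** The cluster size behind the first main hypothesis cannot be obtained from the data collection that the protocol describes. The protocol does not derive 66. The conservative label also points the wrong way: at a fixed intraclass correlation, more smokers per practice means fewer practices, so overstating m understates the requirement. At stake are the stated number of practices for 80% power and the margin left if practices drop out. One entry in the same table also disagrees with its neighbours, and the task list as written has no room for the later measurements on which H1 depends.

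**Working it through.** **Inputs.** Control 12%; intervention 24%, 22%, 20%, 19%; two-sided α = 0.05; power 80%; r = 0.15; m = 66 (all D10). Cards: 100 per assessment, 50 at run-in, 20–25 tobacco users per 100 (Exit Card Surveys). Rounds in the primary analysis: 6 and 12 months (D9). Practices: 40 per arm randomised, 30 to 40 per arm completing (D5).

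**Reproducing the protocol's figures.**

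- The uncorrected sample size per group is n₀ = [1.960·√(2p̄q̄) + 0.842·√(p₁q₁ + p₂q₂)]² / d². For 24% vs 12% this is 159.7, so 160; for 22% it is 221.
- With the continuity correction, n = (n₀/4)·[1 + √(1 + 4/(n₀d))]² gives 176, 240, 354 and 447, exactly as printed. The table is therefore continuity-corrected.
- At m = 66, D = 1 + 65 × 0.15 = 10.75.
- Adjusted n: 176 × 10.75 = 1,892; 240 × 10.75 = 2,580; 354 × 10.75 = 3,805.5; 447 × 10.75 = 4,805.
- Divided by 66: 28.7, 39.1, 57.7 and 72.8 practices, printed as 29, 39, 58 and 73.

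Everything agrees except the third adjusted n, printed as 2,805. The 58 practices beside it support 3,805, since 58 × 66 = 3,828.

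**Cluster size that the plan can deliver.** Post-intervention: 2 × (20 to 25) = 40 to 50. Run-in: 50 cards × 20–25% = 10 to 12.5. Even with the run-in, the maximum is 50 + 12.5 = 62.5.

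**Recalculation by the same method** (practices = n × D / m):

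| | m = 66 | m = 50 | m = 40 |
|---|---|---|---|
| D | 10.75 | 8.35 | 6.85 |
| Effective size per practice, m/D | 6.14 | 5.99 | 5.84 |
| 24% (n = 176) | 28.7 | 29.4 | 30.1 |
| 22% (n = 240) | 39.1 | 40.1 | 41.1 |
| 20% (n = 354) | 57.7 | 59.1 | 60.6 |
| 19% (n = 447) | 72.8 | 74.6 | 76.5 |

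**Power**, with the same continuity correction and an effective n per arm of practices × m/D:

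| | m = 66 | m = 50 | m = 40 |
|---|---|---|---|
| 24% vs 12%, 40 per arm | 91.9% | 91.2% | 90.5% |
| 24% vs 12%, 30 per arm | 81.9% | 80.9% | 79.8% |
| 24% vs 12%, 29 per arm | 80.5% | 79.4% | 78.3% |
| 22% vs 12%, 40 per arm | 81.0% | 79.9% | 78.8% |

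**Timeline.** Enrolment in months 6–10 plus 6 months is months 12–16; plus 12 months is months 18–22. The window of months 7–12 cannot hold any 12-month set, and it holds a 6-month set only for practices enrolled in month 6.

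**The case against.** The strongest reply is that the shortfall depends on the continuity correction. D10 names a chi-square test without mentioning a correction, and D9 plans GEE logistic regression. Uncorrected, 24% vs 12% needs 160 × 8.35/50 = 26.7 to 160 × 6.85/40 = 27.4 practices, and 22% needs 221 × 8.35/50 = 36.9 to 221 × 6.85/40 = 37.8. On that basis the printed 29 and 39 still suffice at m = 40–50. This stands and limits the point: the printed practice numbers are wrong for the method that produced them, but they already contain some slack.

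The value 66 may come from three full sets at 22 smokers each. The protocol does not say so, the run-in has only 50 cards, and baseline cards are outside the primary H1 data. A larger m does raise D and the total number of smokers, which may be why it was called conservative, but what the plan must supply is practices.

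A reader might infer more than the document supports:

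- **That H1 is underpowered.** At 40 per arm, power for the design target stays above 90%.
- **That 22% vs 12% no longer fits.** The need is 40.1 at m = 50, and the protocol itself printed 39.1 as 39. This is a sensitivity column, and the same table already lists 58 and 73 practices, so the protocol never claims that 40 covers every alternative.
- **That m should be cut further for unreturned cards, to about 33–41.** The 20–25 is given per 100 cards in a set, so it probably allows for non-response already. If the follow-up denominators in the DTC.Net advice table are tobacco users, (1,361 + 1,210)/11,600 = 22 per 100 cards, inside that range. The table does not label them, so this supports the reading without proving it.
- **That only one post-intervention set will be collected.** Figure 3's footnote, D8, Table 10, D9 and task 16's own wording all require both rounds; the months cell is a slip.
- **That only about 30–32 practices per arm are expected to finish.** D5 gives 30 to 40.

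The statement that "from 19,000 exit cards distributed for DTC.Net the response rate has been over 85" per cent also disagrees with 15,575/19,000 = 82% in the preliminary data. That is clerical, and the H1 sizing uses neither figure.

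**Conclusion.** The point holds, with a small effect. The planned cards give 40–50 smokers per practice for the primary H1 analysis, so 66 is unreachable and optimistic. By the protocol's own continuity-corrected method the requirement for 24% vs 12% is 30–31 practices per arm rather than 29. For 22% it is about 40–42 rather than 39, at the edge of the 40 randomised. The loss is limited because, at r = 0.15, information per practice is nearly saturated and the effective size falls only from 6.14 to 5.84–5.99. The one place where it matters is the low end of the completion range: with 30 practices per arm, power is about 80–81% and no margin remains.

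The 2,805 entry is an isolated misprint, and the task 16 months contradict the enrolment months. The conclusion assumes that 20–25 per 100 cards is net of non-response and that the intraclass correlation is 0.15, as the protocol states.

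**What to change.** - In D10, restate m as 40–50 and D as 6.85–8.35, show how m follows from the card plan, and remove the conservative label for m.
- Recompute all four columns: 30–31 practices per arm for 24%, about 40–42 for 22%, about 60–61 for 20% and about 75–77 for 19%. State that the sample sizes are continuity-corrected.
- If the m = 66 table is kept for any purpose, correct 2,805 to 3,805.
- In Table 6, extend task 16 from months 7–12 to about month 22, so that it covers both post-intervention rounds.

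The cost is restated figures and one timeline cell. No further practices, patients or cards are needed.
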